### **6.3. Patient replacement**

#### Part A

Patients will be evaluable for DLT, if they received at least 70% of Debio 1143 (i.e., a maximum of 6 missed Debio 1143 doses) and at least one nivolumab dose as planned in Cycle 1 and were evaluated for DLT or if the patient discontinued treatment early due to any toxicity that could be considered a DLT.

Non-evaluable patients will be replaced, as appropriate (see [section 11.5.1](#)).

#### Part B

Patients will be evaluable for efficacy if the following two conditions are met:

- Measurable disease at baseline as per RECIST v1.1 and/or GCIG criteria (Cohort 4, if applicable),
- At least one efficacy assessment, either computed tomography (CT) or magnetic resonance imaging (MRI) for RECIST evaluable patients, or CA-125 dosage performed after baseline, if applicable, or treatment discontinuation occurred before the efficacy assessment was done due to treatment failure, defined as any of the following: death, unacceptable toxicity, clinical deterioration and/or symptoms worsening.

Non-evaluable patients will be replaced.

## **7. CLINICAL SUPPLIES**

### **7.1. Investigational medicinal products**

#### **7.1.1. Debio 1143**

Debio 1143 will be provided by the Sponsor as size 1 hard gelatin capsules (75 mg yellow, 100 mg white opaque) containing API powder along with starch as excipient, for oral administration.

#### **7.1.2. Nivolumab**

Commercially available nivolumab (Opdivo®) will be provided by the Sponsor.

### **7.2. Packaging and storage of IMPs**

Packaging and labeling will be in accordance with applicable local regulatory requirements and applicable Good Manufacturing Practice (GMP) guidelines.

#### **7.2.1. Packaging**

Debio 1143 hard gelatin capsules will be packed in opaque high density polyethylene bottles with a sealed child-resistant closure. Each bottle will contain 10 capsules of either 75 mg yellow capsules or 100 mg white capsules.

Nivolumab (Opdivo®) commercial presentations, 1 x 4 mL vials, 1 x 10 mL vials and/or 1 x 24 mL vials.

#### **7.2.2. Labeling**

Debio 1143 bottles containing 75 mg capsules will have a yellow label, those with 100 mg capsules will have a white one. Commercial pack Nivolumab (Opdivo®) will be overlabelled to dispense study related information as appropriate per local regulations, storage conditions and expiry date in local languages. Label text will comply with local health authority requirements in each participating country.

### **7.2.3. Storage**

Debio 1143 capsules should be stored at a controlled temperature of 15-25°C, protected from direct heat and contact with water. It will be shipped and dispensed at ambient temperature. Do not freeze.

Nivolumab must be shipped and stored at 2-8°C until use. Do not freeze.

### **7.3. Dispensing and accountability of IMPs**

The IMPs and certificates of analysis will be provided to the Investigators by and under the responsibility of the Sponsor, who will also ensure release of the IMPs as per current GMP guidelines. Any documentation required by local health authorities for import of the IMPs will be appropriately submitted.

The Investigator/pharmacist at each study site will inventory and acknowledge receipt of all IMP shipments. The IMPs accompanied by analytical reports when appropriate, must be kept in a locked area with access restricted to designated study personnel, and must be stored in accordance with the manufacturer's instructions.

The Investigator/pharmacist at each study site will keep accurate records of the IMP (and other study-related drugs) dispensed. These records will specify dates and amounts dispensed, to and by whom (drug dispensing list), and report any IMPs accidentally or deliberately destroyed.

Each dispensing of study drug will be documented by recording the patient's number, and date dispensed on the Drug Accountability Form in the electronic case report form (eCRF)/electronic data capture (EDC) system.

At study closure, unused IMPs will be counted and returned to the Sponsor or destroyed with their written permission. Any discrepancies between the IMPs returned and the expected balance must be justified.

Unused IMPs must not be discarded or used for any purpose other than the present study. Throughout the study, the Sponsor's monitor/representative will collect the drug accountability forms along with any unused IMPs in the original packaging.

### **7.4. Patient numbering**

#### **7.4.1. Screening number**

During the screening period (between Day -28 to -1), each potential study patient will be identified by a unique screening number which is displayed when the patient is first recorded in the eCRF via the internet-based application. The screening number allows the patient's data to be entered into the eCRF and subsequently ensures an expedited process when s/he is ready to start the study.

The Screening # consists of a unique 6-digit identifier. The first 3 digits represent the number of the study center and digits 4-5-6 identify the screening order of the subject at the center (starting at 001). Screening #106001, for example, identifies the first subject (001) screened at study center 106. The second subject screened at the same study center will be given Screening # 106002, etc.

If a screened patient fulfils all eligibility criteria and none of the exclusion criteria, the Investigator or designated study coordinator will request enrollment of the patient via the eCRF on study Day 1. Enrollment should not be requested before the patient is fully eligible and ready to start treatment.

### **7.5. Blinding and unblinding methods**

Not applicable, as this is an open-label study.

## **7.6. Method of administration and compliance**

### **7.6.1. Debio 1143**

Debio 1143 capsules are ready to use and will be taken orally once daily for 10 consecutive days every 2 weeks of a 28-day cycle (Days 1 to 10 and Days 15 to 24 q4w).

Patients should fast 2 hours before dosing and should fast at least 1 hour post-dose. Water is permitted freely. Beyond the onsite visits, study medication will be self-administered by patients at home and should be taken at approximately the same time each day. If a dose is forgotten, the patient may take the dose later in the day but no later than 6 h after normal intake time. If the delay exceeds 6 h, the patient must wait until the next scheduled administration. A double dose should not be taken to make up for a missed dose.

If a patient vomits after study medication intake, the patient should not take another dose, but wait until the next scheduled dose. If vomiting persists, the patient should contact the Investigator. Relevant medical instructions should be given to the patient, specifically to not replace any missing doses and to not extend treatment beyond Days 10 or 24, during each cycle for any reason. In addition, the patient should be instructed to record any occurrences of vomiting in the diary card.

Patients' compliance will be verified on Day 1 of each cycle and on days when PK sampling is scheduled during Cycles 1 and 3, if applicable. Compliance will be measured by direct visual supervision at dosing by the Investigator or his/her designee when administered at the hospital, or by means of a diary card to be filled out after each dose when taken at home (the number of capsules, date and time of dosing will be recorded). The diary card will be checked by the Investigator or his/her designee at each study visit. Any change in the daily dosing of Debio 1143, must be appropriately reflected in the patient's diary by the Investigator or his/her designee, such as dose reduction, dose omissions, and treatment resumption, as applicable.

### **7.6.2. Nivolumab**

#### **7.6.2.1. Pre-infusion procedures**

Nivolumab will be administered at 240 mg (flat dose) as an IV infusion, over at least 30 min, on D1 and D15 q4w (1 cycle=4 weeks and two infusions) or 480 mg over at least 60 min, on D1 q4w (1 cycle=4 weeks and one infusion) from Cycle 3.

For instructions on preparation of nivolumab infusion, please refer to locally approved labelling.

A preparation manual will describe in detail the infusion bags and medical devices to be used for the preparation of the dilution and subsequent administration.

Formal premedication is not required. However, premedication might be used after C1D1 administration, if needed, on an individual patient basis, per clinical judgment and local institutional guidelines, as appropriate.

#### **7.6.2.2. Peri- and post-infusion procedures**

For the infusion, patients must be observed according to standard applicable institutional guidelines, if applicable, or for approximately 90 minutes post-infusion, in an area with resuscitation equipment and emergency agents. At all times during nivolumab treatment, immediate emergency treatment of an infusion-related reaction or a severe hypersensitivity reaction according to institutional standards must be assured.

Infusion of nivolumab will be stopped in case of Grade  $\geq 2$  hypersensitivity, inflammatory response, or infusion-related reactions. Infusions may be resumed after Grade  $\leq 2$  events upon resolution of the events within less than 4 hours and after medical assessment and agreement by a qualified Investigator. Infusion duration will not be shorter than 120 minutes after resumption in all subsequent infusions.

Treatment will be withdrawn definitively after the occurrence of any Grade  $\geq 3$  infusion-related reactions, hypersensitivity or cytokine-release syndrome. Appropriate standard measures must be in place for the medical management of the patients under these circumstances.

Recommendations on how to manage infusion-related reactions and severe hypersensitivity reactions according to the NCI are outlined in section 7.6.2.3.

When a reaction does not resolve completely after 4 hours despite appropriate medical management, the ongoing infusion will not be resumed. Upon Investigator judgement and agreement, next scheduled infusions should be performed at a slower infusion rate (i.e., 120-180 minutes) and pre-medications with standard anti-H1, non-steroidal anti-inflammatory drugs (NSAIDs) and/or low dose steroids might be considered as per standard institutional guidelines.

See section 7.6.2.4 for details on the management of immune-related AEs and sections 5.4 and 7.6.2.3 for other (not immune-related) adverse drug reactions (ADRs) potentially requiring nivolumab discontinuation or temporarily withhold.

### 7.6.2.3. Management of infusion-related reactions

Symptoms of infusion-related reactions may be fever, chills, rigors, diaphoresis, hyper or hypotension and/or headache. These symptoms should be managed according to Table 7-1.

**Table 7-1 Treatment modification for symptoms of infusion-related reactions associated with nivolumab**

NCI-CTCAE grade and description	Treatment modification for nivolumab
Grade 1 – mild Mild transient reaction; infusion interruption not indicated; intervention not indicated.	
 
The total infusion time for nivolumab should not exceed 120 minutes.
 

Grade 2 – moderate Therapy or infusion interruption indicated but responds promptly to symptomatic treatment (for example, antihistamines, nonsteroidal anti-inflammatory drugs, narcotics, IV fluids); prophylactic medications indicated for $\leq 24$ h	
 
Stop nivolumab infusion.
 
Resume infusion at 50% of previous rate once infusion-related reaction has resolved or decreased to at least Grade 1 and monitor closely for any worsening.
 

Grade 3 – severe Prolonged (for example, not rapidly responsive to symptomatic medication and/or brief interruption of infusion); recurrence of symptoms following initial improvement; hospitalization indicated for clinical sequelae.	
 
Stop the nivolumab infusion immediately and disconnect infusion tubing from the patient.
 
Patients have to be withdrawn immediately from nivolumab treatment and must not receive any further nivolumab treatment.
 

Grade 4 – life-threatening Life-threatening consequences; urgent intervention indicated.	

If a patient experiences a Grade 3 or Grade 4 infusion-related reaction at any time, the patient must discontinue nivolumab. If an infusion reaction occurs, all details about drug preparation and infusion must be recorded.

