If a patient does not meet the requirements for treatment continuation on any day other than D1 (D2-10 or D15-24) of any cycle, treatment will be immediately interrupted and the corresponding Debio 1143 dose (and nivolumab if on D15) will be omitted. Patients should be re-assessed, ideally, every 48-72 hours, if clinically indicated, and treatment will only be resumed after all re-treatment criteria are met. On D1, treatment can be delayed more than 3 days if required; in this case, the assessment schedule will shift accordingly, and all assessments planned for D1 will be performed on the day treatment is re-started. However, if treatment is interrupted during any day other than D1 and the re-treatment criteria are not met within 72 hours, treatment will be resumed only on D1 of the next cycle.

A maximum delay of 4 and 8 weeks (+1-week tolerance) for Debio 1143 and nivolumab, respectively, is allowed. After this delay-period, treatment will be withdrawn. Patients withdrawing from treatment for any reason will be followed for safety up to 5 months (±15 days) after the last nivolumab infusion, complete resolution or stabilization of any ongoing toxicity, unless the patient starts a new treatment, end-of-life-care or withdraws consent.

Patients experiencing immune-related AEs, that require withholding nivolumab infusions temporarily until resolution to at least Grade 1, may withhold nivolumab for a maximal period of up to 8 weeks (±1 week

tolerance). During this period, patients may continue to receive Debio 1143 as per protocol, if appropriate. Patients requiring more than 8 weeks ( $\pm 1$  week) of nivolumab interruption and those who permanently discontinue nivolumab for any reason, will discontinue Debio 1143 permanently and will be withdrawn from the study. The nivolumab dose will not be adjusted under any circumstances.

Patients experiencing any treatment-related grade 4 toxicity (clinically or laboratory, excluding grade 4 amylases and/or lipase and/or non-febrile neutropenia) will withdraw from treatment definitively without further reduction (see [section 8.3.2.1](#) for details).

Patients experiencing any other treatment-related toxicity fulfilling applicable DLT criteria (as shown below) at any time during the study must stop treatment and may only resume treatment after adequate recovery to re-treatment criteria.

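### Table 7-1 lets a nivolumab infusion restart at residual Grade 1 after a Grade 2 reaction, while section 7.6.2.2 bars a restart if the reaction has not fully resolved after 4 hours

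*Protocol*

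**What the plan says.** Three places in the Protocol govern restarting nivolumab after a Grade 2 infusion-related reaction.

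- **Section 7.6.2.2.** The infusion is stopped for a reaction of Grade 2 or higher. After an event of Grade 2 or lower it may be restarted "upon resolution of the events within less than 4 hours and after medical assessment and agreement by a qualified Investigator". A later paragraph adds: "When a reaction does not resolve completely after 4 hours despite appropriate medical management, the ongoing infusion will not be resumed". The section also sets a 120-minute minimum infusion duration following a restart. It refers onward as follows: "Recommendations on how to manage infusion-related reactions and severe hypersensitivity reactions according to the NCI are outlined in section 7.6.2.3".
- **Synopsis (investigational products, dose and administration).** This gives the same restart conditions and the same 120-minute minimum. It does not contain the separate sentence about incomplete resolution after 4 hours.
- **Section 7.6.2.3 and Table 7-1.** The text says of reaction symptoms: "These symptoms should be managed according to Table 7-1". The Grade 2 row says to stop the infusion, then: "Resume infusion at 50% of previous rate once infusion-related reaction has resolved or decreased to at least Grade 1", with close watch for worsening. The row gives no number of hours and mentions no investigator decision.

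The row definitions in Table 7-1 also matter. Grade 2 is described as "Therapy or infusion interruption indicated but responds promptly to symptomatic treatment". Grade 3 includes reactions that are "Prolonged (for example, not rapidly responsive to symptomatic medication and/or brief interruption of infusion", and leads to permanent withdrawal from nivolumab.

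**The concern.** The Table sets a lower recovery threshold than section 7.6.2.2. It accepts either full resolution or a fall to Grade 1, whereas 7.6.2.2 requires resolution and closes off the restart when resolution is incomplete after 4 hours. The Table is what a nurse or physician is likely to consult during a reaction, and section 7.6.2.3 sends them there.

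What is at stake is patient safety and consistent conduct across sites. Two sites could each follow a written instruction and act in opposite ways on the same patient. One would restart the antibody with symptoms still present, and the other would abandon that day's infusion. Someone working from the Table alone would also not see that an investigator must assess the patient and agree first.

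**Working it through.** No formula applies and the plan gives no figure to reproduce. The check sets the texts side by side.

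**Restart conditions**

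| Condition | Synopsis and 7.6.2.2 | Table 7-1, Grade 2 row |
|---|---|---|
| Recovery | Resolution; 7.6.2.2 adds that incomplete resolution after 4 hours bars a restart | Resolution or a fall to Grade 1 |
| Time | Under 4 hours | No hour figure; prompt response is part of the grade definition |
| Decision | Assessment and agreement by a qualified investigator | Not mentioned |

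The synopsis and 7.6.2.2 state 3 conditions and the Table states 1. That leaves 3 − 1 = 2 conditions absent from the row, and the remaining one is worded more loosely.

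**What each text says to do, case by case**

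1. *Complete resolution before 4 hours.* Both texts allow a restart. The Table adds the half rate; 7.6.2.2 adds assessment and agreement. A site can follow both.
2. *Down to Grade 1 but not gone, before 4 hours.* The Table says restart. Under 7.6.2.2 the answer depends on what resolution means. If it means full resolution, staff must wait. If it means that the event requiring the stop has ended, they need not.
3. *Prompt response, still Grade 1 and not resolved by 4 hours, infusion not yet restarted.* The Table's recovery condition is met, so it says restart. Section 7.6.2.2 says the infusion is not restarted. Because that sentence specifies complete resolution, no interpretation is needed. This is a direct contradiction.
4. *No rapid response to medication or a brief pause.* The Table's own Grade 3 row applies and nivolumab is withdrawn permanently. Section 7.6.2.2 also withdraws treatment for reactions of Grade 3 or higher. There is no conflict over restarting.

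**Which reading of resolution is better in case 2?** The Table lists resolution and a fall to Grade 1 as alternatives, which suggests that they differ. Section 5.4 names the target grade when Grade 1 is enough ("withholding nivolumab infusions temporarily until resolution to at least Grade 1"), so the bare word would mean more. But section 5.4 concerns immune-related events held for weeks, and it also shows the Protocol using the word for a fall to Grade 1. The full-resolution reading is favoured but not settled.

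**Size.** If residual symptoms clear within the limit, following 7.6.2.2 on the full-resolution reading delays the restart by more than 0 and less than 4 hours. If they do not, the rest of that one dose is not given.

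**Infusion duration.** At half rate, a full 240 mg dose planned over 30 minutes takes 30 / 0.5 = 60 minutes, which is below the 120-minute minimum in 7.6.2.2. If that minimum covers the restarted infusion as well as later ones, half rate alone does not satisfy it.

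**The case against.** The strongest reply is that 7.6.2.2 and Table 7-1 are adjacent parts of one section and can be read together: 7.6.2.2 says whether an infusion may restart, and the Table says how. Nothing in the Table tells staff to restart after 4 hours or without agreement. Section 7.6.2.2 is worded as mandatory on this point and introduces 7.6.2.3 as recommendations. The stricter conditions also appear in the synopsis.

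Much of this stands. A reader might infer that the Protocol authorises a restart without investigator agreement, or with no time limit. The documents do not support that: the row only fails to repeat two conditions that 7.6.2.2 supplies. A reader might also infer a conflict for every Grade 2 reaction that falls to Grade 1. That is not supported either. Before 4 hours the conflict rests on one reading of resolution, and there is a fair argument the other way, since 7.6.2.2 stops the infusion only from Grade 2 upward and the Table says a Grade 1 reaction needs no interruption. Nor is the Table open-ended, because reactions that do not respond rapidly move to its Grade 3 row.

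What the reply cannot do is reconcile case 3. Overlaying 7.6.2.2 adds a time limit and a decision-maker, but it does not turn a fall to Grade 1 into complete resolution. Calling 7.6.2.3 recommendations hints at an order of precedence without stating one, and 7.6.2.3 then directs staff to the Table without pointing back.

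**Conclusion.** The concern holds in a narrow form. There is one direct contradiction in a bedside safety rule: a Grade 2 reaction that responds promptly, stays at Grade 1 and has not resolved by 4 hours is to be restarted under Table 7-1 and not restarted under 7.6.2.2. The case should be uncommon, because the Table would usually have led to a restart earlier. For reactions still at Grade 1 before 4 hours, the conflict exists only if resolution means full resolution. The missing time limit and investigator agreement are omissions, made worse by the lack of a cross-reference or stated precedence.

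The consequence for a patient is a restart delayed by less than 4 hours or one incomplete dose, set against restarting with symptoms present. The Table's half rate and close monitoring limit the risk. The frequency of Grade 2 nivolumab reactions is not given, so no count of affected patients is claimed. No endpoint, futility or efficacy boundary, or analysis changes. The correction is still worth making, because the instruction concerns safety and the fix is small.

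**What to change.** Keep the first bullet of the Grade 2 row, which stops the infusion. Replace the second with wording to this effect:

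> Restart at half the previous rate, with close monitoring for worsening, only if the reaction has resolved in under 4 hours and a qualified investigator has assessed the patient and agreed. Otherwise do not restart this infusion. The 120-minute minimum duration in 7.6.2.2 applies after a restart. Section 7.6.2.2 prevails over this table.

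Resolved should be stated to mean completely resolved, in line with the 4-hour sentence in 7.6.2.2. If the sponsor instead intends residual Grade 1 to be enough before 4 hours, the synopsis and 7.6.2.2 should say so.

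The cost is one bullet in one table row, made through the amendment route in section 12.7. It adds no new policy, because the synopsis and 7.6.2.2 already carry the restart conditions and the 120-minute minimum. The downside is that some restarts with residual Grade 1 symptoms will be delayed by less than 4 hours or not completed that day. The SAP needs no change.

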### 7.6.2.4. Management of immune-related adverse events

Since inhibition of PD-1/PD-L1 stimulates the immune system, immune-related AEs may occur. Adequate management and treatment of immune-related AEs provided below is mainly based on American Society

of Clinical Oncology (ASCO) practice guidelines recommendations (35) (but not only), depending upon severity (i.e., NCI-CTCAE grading), in general:

- Grade 1 to 2: treat symptomatically or with moderate dose steroids, more frequent monitoring
- Grade 1 to 2 (persistent): manage similar as to high -grade AE (grade 3 to 4)
- Grade 3 to 4: treat with high dose corticosteroids

Treatment of immune-related AEs should follow ASCO guidelines which are summarized in [Table 7-2](#).

